4.4.2 Replacement of Participants

Enrollment for each study drug arm will be ongoing until all groups within the study drug arm are filled. Participants may be replaced if they withdraw prior to randomization.

4.5 Transfer of Participants between Sites

A participant may request a transfer to a different DIAN-TU site if they relocate or if transfer to a new site will enable improved compliance with all study visits and procedures. Should the trial be closed at a DIAN-TU site, participants from the closing site would be offered the option of remaining in the study and transferring to another site to complete study procedures.

Participants transferring to another site must continue to be administered the same country-specific language and locally adapted cognitive and clinical assessments as they had been completing at their prior site for consistency in data collection.

Participants may have some study procedures performed at other DIAN-TU sites if the procedure cannot be performed at the DIAN-TU site under which they enrolled (e.g., due to equipment failure or PET tracer availability). These participants would remain enrolled at their original DIAN-TU site.

4.6 Expectations and Withdrawal of Sites

Sites are expected to fulfill all study obligations. DIAN-TU sites that fail to fulfill study obligations may be terminated from the study. While a site is on probationary status or if a site is terminated, participants at that site will be offered the option of transferring to a different DIAN-TU site on a temporary or, if the site is terminated, permanent basis. After obtaining signed release from participants, copies of all source documents should be made available to the new site as rapidly as possible and at least within 30 days after probationary status begins.

5 STUDY DRUGS

See each drug-specific appendix for drug-specific background, preclinical and clinical data, rationale for specific biomarkers endpoints to assess target engagement, risks/benefits and specifics of drug packaging, preparation, administration, compliance, analysis issues, and drug-specific adverse events, and schedule of visits.

The following information on blinding, concomitant medications, and treatment compliance applies to all drugs.

5.1 Blinding

During double-blind periods, participants and study staff will remain blinded as to whether participants are on active drug or placebo. Participants and staff will not be blinded as to the treatment route and interval. The procedures taken to maintain blinding are detailed in each drug-specific appendix and/or associated *DIAN-TU Pharmacy Manual*.

During double-blind periods in which non-carriers are eligible to participate, genetic status will not be disclosed to either the participant or study staff. Mutation positive participants may already be aware of their genetic status and choose to disclose this to study staff. The mutation positive participants will be encouraged not to disclose their genetic status to study staff. For participants who have not been provided with their mutation status, the staff will be encouraged not to make assumptions about genetic status or group assignment within a study drug arm when adverse events (AEs) are reported. Genetic status will be confirmed for entry into any OLE period.

Should any drug arm continue into an open-label extension period, treatment assignment from the double-blind period may remain blinded to investigators and participants based on the goals of the OLE period.

5.2 Breaking the Blind

With the exception of the periodic DSMB data review or required regulatory reporting for expedited reports by designated safety personnel who do not have contact with study staff or participants, the study blind will not be broken until all participants in a blinded study drug arm have completed the double-blind treatment period and the database for that study drug arm is locked. Only in the case of an emergency, when knowledge of the study drug is essential for the immediate clinical management or welfare of a specific participant, may the investigator unblind a participant's treatment assignment.

Prior to any unblinding, the investigator is strongly advised to discuss options with the PAL, Medical Director or designee. As soon as possible, and without revealing the participant's study drug assignment (unless important to the safety of participants remaining in the study), the investigator must notify the sponsor if the blind is broken for any reason and the investigator was unable to contact the sponsor prior to unblinding. The investigator will record in source documentation the date and reason for revealing the blinded treatment assignment for that participant.

5.3 Concomitant Medications

All concomitant medication taken during the study must be recorded on the Concomitant Medication electronic case report form (eCRF). Participants will be instructed to consult the investigator or other appropriate study personnel at the site before initiation of any new medications or supplements and before changing dose(s) of any current concomitant medications or supplements.

To approximate standard of care for AD, use of certain approved treatments for AD is permitted in this study, but use of additional anti-amyloid therapies i.e. Aduhelm™ (aducanumab), are exclusionary and may not be used during trial participation. This section provides additional guidance on managing concomitant medication use during the trial. Before starting any Alzheimer's disease medication, participants should be informed to discuss with their site study team, and sites should discuss with the sponsor, to determine if the medication use affects the participant's continued eligibility. Taking a drug that conflicts with the trial design may exclude continued participation, e.g., taking an approved anti-amyloid treatment while participating in an anti-amyloid study treatment arm.

Allowed Medications. Use of the following approved treatments for AD is permitted during the study, provided that such medications have been given for at least 90 days and the dose has been unchanged for 2 months (60 days) before CRI Entry and Visit 2: donepezil (Aricept®), rivastigmine (Exelon®), galantamine (Razadyne®, Razadyne®ER), and memantine (Namenda®). Doses of these medications should remain constant throughout the study.

If a participant has recently stopped acetylcholinesterase inhibitors (AChEIs) and/or memantine, he or she must have discontinued treatment at least 90 days before CRI Entry and

Visit 2. Other vitamins or nutraceuticals given for their possible effects on AD may be continued on stable doses beginning 90 days before CRI Entry and Visit 2.

Starting, stopping, or changing doses of AChEIs and/or memantine during the study might interfere with outcome measures and therefore could result in discontinuation of the participant from the study.

Before a participant starts, stops, or changes doses of AChEIs and/or memantine or other treatments for their AD, the PAL, Medical Director or designee should be contacted to determine whether or not the participant should continue in the study and whether or not clinical outcome measures should be performed. It should be documented if sponsor discussion and approval in advance of starting, stopping, or changing doses is in place prior to any change. Changes may be tracked as a protocol deviation for analysis purposes.

If changes are made without prior contact with the PAL, Medical Director or designee, the principal investigator/sub-investigator, once informed of these changes, should contact the PAL, Medical Director or designee to discuss and jointly determine whether or not the participant should continue in the study and whether or not clinical outcome measures should be performed. It will be a protocol deviation if discussion and sponsor approval prior to the start, stop, or modification of such medications were not in place.

Non-medication treatments for AD such as psychotherapy are permitted but are subject to the same restrictions as medication treatment taken for AD.

Other concomitant medications that affect CNS function may be given if the dose remains unchanged throughout the study. Doses of these compounds should remain constant from 4 weeks before CRI Entry and 4 weeks before baseline (Visit 2).

To avoid effects on cognitive measures, participants should not stop receiving any medications that affect CNS function during the study, add any to the treatment regimen, or change doses of these medications. If unforeseen starting, stopping, or changing of stable doses of these drugs occurs during the study, the PAL, Medical Director or designee must be contacted to determine whether or not the participant should continue in the study and whether or not outcome measures should be performed.

Use of benzodiazepines for treatment on an as-needed basis for insomnia or daily dosing as anxiolytics is permitted. Use of sedatives or hypnotics should be avoided for 8 hours before administration of the cognitive tests unless they are given chronically.

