6.3.7 Early Termination Visit and Post-treatment Follow-up Period

If a participant withdraws, is terminated from the study prior to completion of a treatment period, or is in a study drug arm that is stopped prior to the end of the treatment period, every effort should be made to schedule an early termination visit. PET imaging studies may be omitted if early termination occurs less than 6 months after the previous PET imaging or if precluded by local regulations/dosimetry limits. Other procedures may also be eliminated on a case-by-case basis, as determined by the sponsor or if not required based on the study drug arm procedures or study period.

Any participant that meets study drug discontinuation criteria per Section 4.4.1 (excluding participants who are known mutation negative) will be encouraged to continue participation in any of the scheduled clinical, cognitive, and/or biomarker assessments that are able to be performed even though dosing has concluded. The determination of which assessments to be attempted/completed will be decided with the site principal investigator and sponsor based on the participant's capabilities, the benefit to the study, and the risk associated with continued participation at the time of study drug discontinuation. The level of continued participation may change if/as the participant's status changes.

Location: DIAN-TU site or at the participant's home or other trial-identified location with the trial-designated home health nurse

Time/Timing: The early termination visit may occur at any time during the study. Approximately a 3- to 4-day visit. For participants who live near the study site, these visit procedures may be scheduled over a longer time period of up to 2 weeks.

Procedures: See each drug-specific appendix for the specific assessments that are required at each visit. Procedures may include any of the following:

- Medical/treatment history, including:
 - Concomitant medications
 - Assessment /recording of adverse events
- Laboratory sample collection (drug-specific tests, stored plasma and/or serum, and clinical safety assessment)
- Administration of C-SSRS
- Vital signs (blood pressure, heart rate, respiratory rate, body temperature, weight and height)
- Physical and neurological examinations
- Clinical assessments:
 - CDR including calculation of CDR-SB
 - NPI-Q
 - GDS

- FAS
- MMSE
- Assessment of clinical diagnosis and clinician judgment of symptoms.

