4.2.18	Subjects with clinically significant deficiency in B12 (recent diagnosis or in active treatment)	UDS Form Neurological Exam (Item 8, 9) UDS Form A5 Subject Health History (Item 5d)	NXSENSOR (2) and NXTENDON (2) and B12DEF (1)

Author: [REDACTED]

Version Number:

7

Version Date:

07Dec2023

Template No.: CS_TP_BS016 Revision 6

Reference: CS_WI_BS005

Effective Date: 02Dec2019

When subjects meet the criteria above (per the respective DIAN-OBS data freeze corresponding to the analysis) to be included in the DIAN-TU-001 primary analysis, selected secondary, and selected sensitivity analyses, only their data from the point of eligibility and thereafter will be included.

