5.4.3. MAIN SET CONTROLS

The main set controls are defined as the external controls plus the internal set controls.

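### Protocol 5.3 lets outcome measures be stopped, without criteria, after a change of AD or CNS-active medication, which can censor worsening participants informatively in the CDR progression analyses

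*Protocol*

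**What the plan says.** Protocol Section 5 introduces its general rules with "The following information on blinding, concomitant medications, and treatment compliance applies to all drugs". They therefore cover the double-blind arms, and Appendix 3 states no exception for the gantenerumab OLE.

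Protocol 5.3 warns: "Starting, stopping, or changing doses of AChEIs and/or memantine during the study might interfere with outcome measures". It adds that such a change "therefore could result in discontinuation of the participant from the study". If a change to AD medication was made without prior contact, the investigator and sponsor are to "jointly determine whether or not the participant should continue in the study and whether or not clinical outcome measures should be performed". The sentence on changes discussed in advance gives the same choice. For other CNS-active drugs the sponsor's medical team is contacted "to determine whether or not the participant should continue in the study and whether or not outcome measures should be performed". No criteria are given in any of the three places.

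Protocol 6.3.7 says that participants who meet study-drug discontinuation criteria "will be encouraged to continue participation in any of the scheduled clinical, cognitive, and/or biomarker assessments", with the scope settled between site and sponsor.

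In the SAP:

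- Sections 16.2.3.1 (CDR-SB) and 16.2.3.2 (CDR Global) censor participants without progression at their last measurement. A rise must be seen at two consecutive measurements, except that a rise at the last measurement counts by itself.
- Section 7.3 allows no imputation.
- Section 13 counts participants with AD medication changes during the OLE. No analysis uses those changes.
- Section 5.4.3: "The main set controls are defined as the external controls plus the internal set controls". Internal controls (5.4.2) are double-blind placebo participants of this trial who did not enter the OLE. For DIAN-OBS participants, "only their data from the point of eligibility and thereafter will be included" (5.4.1).

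**The concern.** A common reason to start an AD medication is that the participant is getting worse. If outcome measures are then stopped, the decision to stop observing depends on the outcome itself. Non-informative censoring, which the Cox models assume, then fails.

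The full CDR is annual in the OLE (weeks 48, 104 and 156; Appendix 3, 3.2.5). Symptoms, a medication start and a decision not to test can therefore all fall between two CDRs. If no later CDR is done, a participant who was CDR 0 is censored event-free at that earlier visit. In the OLE the decision is made with treatment known (Appendix 3, 2.4).

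At stake are the two interim primary analyses (SAP 17): CDR Global and CDR-SB progression in baseline-asymptomatic participants, All Gant exposure mITT against main set controls. The question is whether the rule acts equally on both sides of that comparison.

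**Working it through.** **No figure to reproduce.** The documents give no event count, power or expected hazard ratio for the CDR comparison, and no frequency of use of the 5.3 clause. What follows is an illustration with no true drug effect.

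**Who is under the rule**

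- Gantenerumab participants: yes, in both periods.
- Internal placebo controls: yes, through Section 5. The wording in force earlier in the double-blind period cannot be checked, because only the current protocol is to hand. Their number is limited: 40 carriers were in the pooled placebo group (Protocol 3.3), and only those who did not enter the OLE count as internal controls.
- DIAN-OBS controls: not stated. SAP 5.4.1 matches them on entry criteria. Protocol 3.2 says only that DIAN-OBS follows nearly the same protocol.

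**Inputs (assumed).** Annual CDR; constant progression hazard h of 0.1 or 0.2 per year; a share q of progressors lose the CDR that would have shown the rise; a share f of controls is under the same rule.

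**Case 1: the decisive CDR and all later CDRs are lost.** The chance of progressing per interval is p = 1 − exp(−h), which is 0.0952 for h = 0.1 and 0.1813 for h = 0.2. Without loss, events per person-year of observed follow-up equal p. With loss, events fall to (1 − q) of their number, and each lost progressor gives up one year of follow-up. The rate becomes p(1 − q)/(1 − qp). The apparent ratio is

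[(1 − q)/(1 − qp)] × [(1 − fqp)/(1 − fq)].

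For h = 0.1, q = 0.1, f = 0: 0.9/(1 − 0.00952) = 0.91. For q = 0.3, f = 0.3: (0.7/0.9714) × (0.9914/0.91) = 0.79.

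**Case 2: only one CDR is missed and the next is done** (3 years, f = 0). The event is recorded a year late, and is lost only if the missed visit is the third. For h = 0.1 the first-event probabilities at visits 1 to 3 are 0.0952, 0.0861 and 0.0779, giving 0.2592 events over 2.7236 person-years. At q = 0.3:

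- events: 0.2592 − 0.3 × 0.0779 = 0.2358
- person-years: 2.7236 + 0.3 × (0.0952 + 0.0861 − 0.0779) = 2.7546
- ratio: (0.2358/2.7546)/0.0952 = 0.90

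**Results (h = 0.1 / h = 0.2)**

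| q | Case 1, f = 0 | Case 1, f = 0.3 | Case 1, f = 1 | Case 2, f = 0 |
|---|---|---|---|---|
| 0.1 | 0.91 / 0.92 | 0.93 / 0.94 | 1.00 | 0.97 / 0.97 |
| 0.2 | 0.82 / 0.83 | 0.86 / 0.87 | 1.00 | 0.93 / 0.93 |
| 0.3 | 0.72 / 0.74 | 0.79 / 0.80 | 1.00 | 0.90 / 0.90 |

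Simulated Cox models with 60 treated and 100 controls over 3 years show the same pattern for Case 1. Median hazard ratios were 0.89–0.91, 0.79–0.84 and 0.70–0.75 with f = 0, and about 0.92, 0.85 and 0.75–0.78 with f = 0.3.

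**Case 3: measures are stopped after the rise is recorded.** The ratio for first progression stays at about 1.00, because a rise at the last measurement counts. Later recurrent CDR-SB events can still be cut off; that effect was not computed.

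**The case against.** The strongest reply is that three stronger readings, which a reader might infer, are not supported.

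- *The controls have no such rule.* This is wrong for the internal controls, who are placebo participants of the same trial. It is unproven for DIAN-OBS, where the documents are silent.
- *Progressing participants are removed.* The decision is optional and its usual effect is censoring. A participant leaves the mITT set only if no post-baseline CDR Global exists.
- *Section 5.3 contradicts 6.3.7.* It does not. Section 6.3.7 encourages continued assessment and leaves the scope to site and sponsor, which is similar discretion.

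There are also safeguards. One skipped CDR only delays an event if a later CDR is done. A discontinued participant should have an early termination visit with the week-156 procedures, including CDR (Appendix 3, 3.2.8), and SAP 6.3 assigns such data to the annual visit within 6 months. Treatment is known only in OLE time, while the All Gant exposure set also includes double-blind time. The final primary endpoint, PiB-PET without controls, is not part of this comparison.

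Last, the interim data cut was 31 March 2023 (SAP 4.3) and this protocol is dated 05 Apr 2023, so rewording 5.3 cannot change those data.

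All of this stands and limits the point. It does not remove the discretion, supply criteria for using it, or show that DIAN-OBS controls are subject to the same practice.

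**Conclusion.** The concern holds in a limited form. Section 5.3 permits outcome collection to stop for a reason related to worsening, and the SAP handles this only by censoring at the last CDR. Informative censoring is therefore possible in the CDR progression analyses. Its balance against the DIAN-OBS controls is not shown, and if treated participants lose more decisive visits than controls do, the bias favours gantenerumab.

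The size cannot be determined from the documents. Under the assumed rates, with 10% to 30% of treated progressors affected, the apparent ratio runs from about 0.9 to 0.7 when all later CDRs are lost and no controls are under the rule. It runs from about 0.94 to 0.75 when 30% of controls are, and from about 0.97 to 0.90 when only one visit is missed. It is about 1.0 if all controls are under the same rule. Neither the share affected nor the share of internal controls is stated.

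**What to change.** **Protocol 5.3.** In both AD-medication sentences, delete the clause that puts the performance of clinical outcome measures up for decision, and delete the matching clause in the CNS-drug paragraph. State instead that scheduled assessments are performed regardless of any start, stop or change of these medications, and that the change is recorded. Whether study drug or participation continues after such a change stays with the protocol's existing process. This acts on remaining and later arms, for which Protocol 3.1 plans to use platform placebo and DIAN-OBS controls.

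**OLE SAP.**

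- Report, by group, the CDR assessments not performed because of a 5.3 decision.
- Add a sensitivity analysis of the CDR progression endpoints that cuts follow-up at the first AChEI or memantine change in treated participants and controls alike, where DIAN-OBS medication data allow. Table A already uses the DIAN-OBS medication form, but only for an anticoagulant exclusion, so the availability of start dates must be checked. This analysis cannot recover CDRs that were never done, which is why the count is also needed.

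**Cost.** Protocol wording, one table and one sensitivity analysis; no new visits. The downside is that some scores will reflect symptomatic medication.

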5.4 Treatment Compliance

Compliance will be monitored for all drugs and recorded on study documents. See each drug-specific appendix for specific compliance monitoring for each study drug.

6 STUDY PROCEDURES

The procedure schedule described in this section includes any procedures that may be performed in treatment arms and/or CRI periods. The inclusion of specific procedures and timing for completion are described in the respective protocol appendices.

6.1 Procedures

6.1.1 Participant Informed Consent

Prior to any study procedures or study-related activities, an IRB or IEC approved Informed Consent Form (ICF) must be signed and dated by the participant (and/or caregiver/legally authorized representative if the participant is cognitively impaired) and by the study partner (if required). Study staff must document the informed consent process in the participant's source document. A copy of the signed and dated ICF will be provided to the participant and study partner.

Because of the complexity of this study design, informed consent may occur in two steps when more than one drug is recruiting simultaneously. In addition, a separate informed consent will be obtained for CRI and/or OLE periods.

For participants enrolling into the CRI period, an ICF specific to the CRI period will be used. The CRI ICF will provide detailed information on study design, duration, number and timing of visits and procedures, and potential side effects associated with drugs that target amyloid- β or tau, and intent for participants to enroll in a study drug arm when one becomes available. It will also include the main requirements of future potential drug arm(s) (e.g., duration, frequency of procedures, etc.). The CRI ICF will explain that participants who continue to meet eligibility criteria may be randomized to a study drug arm once a drug arm is open. The ICF should be clear that there is the potential to be excluded from the study drug arm if any entry criteria are not met and it is in the best interest of the participant not to participate. Participants will be re-consented prior to enrollment to a study drug arm.

For participants enrolling into a treatment period when more than one drug arm is enrolling, a main ICF and supplemental drug-specific ICF may both be used. The main ICF will include a description of the overall study including an overview of possible side effects of the study drugs and differences between study procedures for the different study drug arms. Participants signing the main ICF agree to screening and randomization and indicate their intention to enter the study. After randomization, a supplemental study drug arm-specific ICF document may be reviewed with and signed by the participant (and/or caregiver/legally authorized representative if the participant is cognitively impaired). This supplemental ICF will contain additional details about the procedures, risks and benefits of the specific study drug arm. Participants and their caregivers will have the opportunity to review the main and all supplemental ICFs before they sign the main study informed consent. This two-step approach is needed to keep the ICF concise as participants will only be assigned to one study drug arm, and also keeps confidential

drug information in separate documents. In cases where only one drug is enrolling, one informed consent may be used in a more traditional fashion.

The ICFs must be written in a language fully understood by the prospective participant, study partner, and caregiver/legally authorized representative (if the participant is cognitively impaired). The investigator or designee shall give the participant adequate opportunity to read the ICF before it is signed and dated. Information will be given in both oral and written form, whenever possible, and in the manner deemed appropriate by the IRB/IEC. Participants must also be given ample opportunity to inquire about details of the study.

If eligibility criteria for an open-label extension period are met, a new written ICF will be obtained from the participant, study partner (if applicable) and/or by the participant's legally authorized representative accordingly.

The opportunity to donate post-mortem brain tissue will be discussed. Interested participants will be provided additional details and a brain donation informed consent will be signed. The DIAN-TU Neuropathology Core (DIAN-TU NPC) will conduct a neuropathologic assessment of each participant recruited to the DIAN-TU who consents to a brain donation and comes to autopsy. Each participating DIAN-TU center will coordinate with the DIAN-TU-NPC to ensure that a brain donation is successful, and that tissue will be preserved (freezing the right half of the brain and fixing the left hemibrain in formalin according to the DIAN-TU NPC manual instructions) and subsequently transported to the DIAN-TU-NPC. To ensure standardized methods and uniform assessment of tissue across DIAN-TU sites, the DIAN-TU sites and NPC will undertake a neuropathologic assessment as described in the *DIAN-TU Brain Donation and Neuropathology Program Manual*.

